10.1.5 Time at risk in subject-years by COVID-19 pandemic period

In this section, “study drug” refers to BKZ treatment.

10.1.5.1 Time at risk in the pre-COVID-19 pandemic period

Only study participants starting study drug during the “pre-COVID-19 pandemic period” will have a time at risk calculated during that period. The following rules will be applied:

- For study participants who did not discontinue medication in the “pre-COVID-19 pandemic period” (ie, for study participants with date of last dose of study drug on or after 11Mar2020):

$$10\text{Mar}2020 - \text{date of first dose} + 1$$

- For study participants who have died on or before 10Mar2020:

$$\text{date of death} - \text{date of first dose} + 1$$

Note: If the date of death is later than 140 days following the last dose of BKZ, this rule does not apply, and the duration of exposure will follow the rule below.

- For study participants who discontinued medication in the “pre-COVID-19 pandemic period” (ie, for study participants with date of last dose of study drug before 11Mar2020):

- If the earliest date between (date of last dose + 140) and (date of last clinical contact) is on or after 11Mar2020, then:

$$10\text{Mar}2020 - \text{date of first dose} + 1$$

- If the earliest date between (date of last dose + 140) and (date of last clinical contact) is before 11Mar2020, then use the minimum of:

- date of last dose + 140 – date of first dose +1
 - date of last clinical contact – date of first dose +1

10.1.5.2 Time at risk in the COVID-19 pandemic period

This period is applicable for all study participants in the SS who are still considered at risk on the 11MAR2020 (ie, those who have their first dose is on or after 11MAR2020, or for those for whom either dosing is continuing, or for whom the 140 day SFU period after last dose has not

been completed [in the case of premature treatment discontinuation or for those who do not roll over to the OLE]). The following rules will be applied:

- For study participants who started IMP prior to 11MAR2020 and did not discontinue medication in the “during COVID-19 pandemic period” (ie, for study participants with the last dose of BKZ 160mg is on or after the date of the end of the pandemic +1):

$$\text{date of the end of pandemic} - 11\text{Mar}2020 + 1$$

- For study participants who started IMP on or after 11MAR2020 and did not discontinue medication in the “during COVID-19 pandemic period” (ie, for study participants with the last dose of BKZ 160mg is on or after the date of the end of the pandemic +1):

$$\text{date of the end of pandemic} - \text{date of first dose} + 1$$

- For study participants who have died on or after 11Mar2020, and on or before the pandemic end date:

$$\text{date of death} - \text{maximum (11MAR2020, date of first dose)} + 1$$

Note: If the date of death is later than 140 days following the last dose of BKZ, this rule does not apply.

- For study participants who discontinued medication:

- in the “pre-COVID-19 pandemic period” (ie, for study participants with date of last dose of study drug before 11Mar2020), and if the earliest date between (date of last dose + 140) and (date of last clinical contact) is on or after 11Mar2020, then use minimum between:

- date of last dose + 140 – 11Mar2020 +1
 - date of last clinical contact – 11Mar2020 + 1

- in the “during COVID-19 pandemic period” (ie, for study participants with date of last dose of study drug on or after 11Mar2020, and on or before the pandemic end date),

- For study participants who started IMP prior to 11MAR2020, and if the earliest date between (date of last dose + 140) and (date of last clinical contact) is after the end of pandemic, then use:

$$\text{date of end of pandemic} - 11\text{MAR}2020 + 1$$

- For study participants who started IMP on or after 11MAR2020, and if the earliest date between (date of last dose + 140) and (date of last clinical contact) is after the end of pandemic, then use:

$$\text{date of end of pandemic} - \text{date of first dose} + 1$$

- Else time at risk will be calculated as minimum between:

- date of last dose date + 140 – maximum (11MAR2020, date of first dose) + 1
 - date of last clinical contact – maximum (11MAR2020, date of first dose) + 1

10.1.5.3 Time at risk in the post-COVID-19 pandemic period

This period is applicable for all study participants in the SS who are still considered at risk on the day after the end date of the pandemic (ie, those for whom either dosing is continuing or for

whom the 140 day SFU period after last dose has not been completed [in the case of premature treatment discontinuation or for those who do not roll over to the OLE)]. The following rules will be applied:

- For study participants who did not discontinue medication in the “during COVID-19 pandemic period” (ie, for study participants with date of last dose of study drug after the pandemic period end date), then use minimum between:
 - $\text{date of last dose} + 140 - \text{date of the end of pandemic}$
 - $\text{date of last clinical contact} - \text{date of the end of pandemic}$
- For study participants who have died after the *pandemic end date*:
$$\text{date of death} - \text{date of the end of pandemic}$$

Note: If the date of death is later than 140 days following the last dose of BKZ, this rule does not apply.

- For study participants who discontinued medication in the “during COVID-19 pandemic period” (ie, for study participants with date of last dose of study drug on or before the pandemic period end date), and if the earliest date between (date of last dose + 140) and (date of last clinical contact) is after the pandemic period end date, then use minimum between:
 - $\text{date of last dose} + 140 - \text{date of the end of pandemic}$
 - $\text{date of last clinical contact} - \text{date of the end of pandemic}$

To assess the impact of the COVID-19 pandemic, the study medication duration and time at risk will be reported by COVID-19 pandemic period.

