10.2.4 Impact of COVID-19

To assess the impact of the COVID-19 pandemic on safety, additional summaries and listings will be presented.

For reporting purposes, AEs will be assigned to either Pre-COVID-19, COVID-19 or post-COVID-19 pandemic period by comparing the AE start date (based on imputed date) to the COVID-19 pandemic period start and end dates (Section 3.2.2.2) (AE allocated to a period if it starts during the period):

The following categories of TEAE will be summarized by MedDRA SOC, HLT and PT, including EAIR and EAER:

- All TEAEs by time of onset relative to COVID-19 pandemic period (prior/during/post) by region and overall
- All serious TEAEs by time of onset relative to COVID-19 pandemic period (prior/during/post) by region and overall
- All TEAEs leading to study discontinuation by time of onset relative to COVID-19 pandemic period (prior/during/post) by region and overall
- All TEAEs leading to permanent withdrawal of study medication by time of onset relative to COVID-19 pandemic period (prior/during/post) by region and overall

- All COVID-19 related TEAEs by treatment group, region and overall

COVID-19 related TEAEs will be identified by searching for Preferred Terms “Corona virus infection” and “Coronavirus test positive”. These will include confirmed or suspected COVID-19 infections. All the above table summaries will be produced on the overall period, except for the summary on the COVID-19 related TEAEs that will be produced for all treatment periods.

A separate listing of all COVID-19 related AEs will be presented, where COVID-related AEs are identified as described above.

In addition, all listing of AEs will include a column for COVID-19 relatedness (as defined above) and the time of onset of each AE relative to the COVID-19 pandemic.

For the purpose of calculating EAIR and EAER by COVID-19 pandemic period, the calculation of exposure time at risk presented in Section 10.1.5 will be used. An individual study participant may therefore be counted in the denominator for several COVID-19 pandemic periods dependent on whether the study participant is still considered at risk on the COVID-19 pandemic start and stop dates. In this case time at risk will be calculated separately for each period.

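### SAP 10.1.5.3 gives the wrong bimekizumab time at risk, in a direction that depends on the reading, when the first bimekizumab dose falls after the declared end of the pandemic

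*SAP*

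**What the plan says.** All references are to the SAP. Section 10.1.5 opens: "In this section, “study drug” refers to BKZ treatment". Section 10.2.4 states that, for EAIR and EAER by pandemic period, "the calculation of exposure time at risk presented in Section 10.1.5 will be used".

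- **10.1.5.1 (before the pandemic)** is tied to bimekizumab start: "Only study participants starting study drug during the" pre-pandemic period have time calculated there.
- **10.1.5.2 (during)** expressly admits "those who have their first dose is on or after 11MAR2020". Two of its branches choose the clock start by when IMP began. The first reads "For study participants who started IMP prior to 11MAR2020 and did not discontinue medication in the" pandemic period, and counts from 11 March 2020. A sub-rule does the same for participants whose last dose fell during the pandemic and whose risk period runs past its end. The death rule and the residual rule instead use the later of 11 March 2020 and the first dose.
- **10.1.5.3 (after)** applies to participants "still considered at risk on the day after the end date of the pandemic", explained as dosing continuing or the 140-day follow-up not completed. Every formula subtracts the pandemic end date. There is no provision for a first dose inside the period and no maximum against the first dose.

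Section 3.2.2.2 uses the post-pandemic period only if the WHO declares an end before the study ends, and records that none had been declared when the SAP was finalised.

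**The concern.** Placebo participants move to bimekizumab at Week 16, and about 100 of the 300 planned participants are in that arm. Section 10.2 assigns an adverse event to the treatment received at onset, and 10.2.4 assigns it to a pandemic period by onset date. A bimekizumab rate for a period therefore needs a denominator that starts at the later of the period start and the first bimekizumab dose.

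Section 10.1.5.3 does not provide this for a first bimekizumab dose after the pandemic end. Either the participant's time is left out while the events stay in, or placebo days come in without placebo events. The tables exist to compare rates before, during and after the pandemic, and either error distorts that comparison.

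**Working it through.** The SAP gives no figure to reproduce. The check applies its date rules to example participants.

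**Inputs.** Switch at Week 16 = 112 days (2.3). Last planned dose at Week 48 = 336 days (section 7). Week 52 = 364 days. Follow-up 140 days after the last dose (10.2). Visit window ±4 days after Week 16 (3.1). The SAP is based on a protocol amendment dated 16 February 2021 (section 1). Pandemic end dates below are assumptions.

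**1. Section 10.1.5.3, switcher still on placebo at the pandemic end.** First placebo dose *d* days before the end, last contact at Week 52.
- Correct bimekizumab time: 364 − 112 + 1 = 253 days.
- Formula as written: 364 − *d* days.
- Excess if placebo counts as dosing: 364 − *d* − 253 = 111 − *d*. For *d* = 0, 1, 30, 60, 100 this is 111, 110, 81, 51, 11 days.
- If only bimekizumab counts, the participant is not at risk on the day after the end and contributes 0 days instead of 253.

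**2. Section 10.1.5.3, participant randomised to bimekizumab with first dose 30 days after the end.**
- Correct: 364 + 1 = 365 days.
- Applicability sentence applied: 0 days.

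**3. Section 10.1.5.2, can the two IMP-based branches be reached?** An affected switcher began placebo by 10 March 2020 and bimekizumab on or after 11 March 2020.
- Latest Week 48 dose: 10 March 2020 + 336 days = 9 February 2021, or 13 February 2021 with the window.
- Any declared end is later than 16 February 2021 (sections 1 and 3.2.2.2).
- The first branch needs the last dose after the end, so no on-schedule switcher reaches it.
- The sub-rule needs the last dose + 140 days (and last contact) to pass the end. 9 February 2021 + 140 = 29 June 2021, and 13 February 2021 + 140 = 3 July 2021. It matters only if the end falls before about July 2021.
- Example with an assumed end of 31 May 2021: placebo from 10 March 2020, bimekizumab from 30 June 2020, followed to 29 June 2021. As written, 11 March 2020 to 31 May 2021 = 447 days. From first bimekizumab, 30 June 2020 to 31 May 2021 = 336 days. Excess 447 − 336 = 111 days.
- With a late assumed end (1 January 2023), the residual rule applies and the excess is 0, provided *first dose* there means first bimekizumab dose.

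**4. Scale, on the placebo-counts reading.**
- One affected switcher entering the extension: 253/(253 + 111) = 0.695 at the maximum, and 253/(253 + 55) = 0.821 at about half the maximum.
- With safety follow-up instead, bimekizumab time is 224 + 140 + 1 = 365 days: 365/(365 + 111) = 0.767 and 365/(365 + 55) = 0.869.
- Pooled illustration, with all time in one period and full follow-up: 200 × 365 + 100 × 253 = 98,300 days. With 111 excess days each, 5 affected switchers give 98,300/98,855 = 0.994 and 50 give 98,300/103,850 = 0.947. A post-pandemic period holding less total time would be diluted more by the same number of switchers.

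**The case against.** Several objections stand. Most of 10.1.5.2 is already guarded: the death and residual rules take a maximum, and the branch beginning "For study participants who started IMP on or after 11MAR2020 and did not discontinue medication in the" pandemic period, with its matching sub-rule, starts at the first dose. The first IMP-based branch cannot be reached on schedule. The post-pandemic period may never be used. The standard adverse event tables use 10.1.1 to 10.1.3, which treat switchers separately. For EAIR, participants with the event contribute time to first occurrence (10.2), so time-at-risk errors enter only through those without it.

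A reader might infer that untreated days generally enter the bimekizumab denominator and that rates are therefore too low. The documents do not support this. The sentence in 10.1.5.3 restricts who is counted, and with study drug defined as bimekizumab its literal effect is to omit time, which raises rates. The too-low direction needs placebo to count as continuing dosing.

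A reader might also take ratios such as 0.695 to 0.869 as the bias in a reported rate. They describe one affected participant. The pooled effect depends on how many are affected, and the SAP gives no enrolment dates.

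These points narrow the finding but do not remove it. Neither reading of 10.1.5.3 gives the right time for a first bimekizumab dose after the pandemic end.

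**Conclusion.** The point holds, at minor severity. Section 10.1.5.3 is wrong as written for anyone whose first bimekizumab dose comes after the declared pandemic end. The strict reading gives zero time at risk and rates that are too high. The reading in which placebo is dosing adds up to about 111 placebo days per switcher and gives rates that are too low.

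The mixing of IMP and bimekizumab in 10.1.5.2 is a smaller inconsistency. It matters only through the sub-rule, and only if the end is declared before about July 2021.

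The conclusion assumes that an end is declared before the study ends and that some first bimekizumab doses fall after it (in 10.1.5.2, after 11 March 2020). It is confined to the descriptive pandemic-period exposure and EAIR/EAER tables. Neither the direction nor the size of the pooled effect can be fixed from the SAP.

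**What to change.** - **10.1.5.3, formulas:** replace the pandemic end date with maximum(pandemic end date, date of first BKZ dose − 1) in all of them. The −1 makes the first bimekizumab day count.
- **10.1.5.3, applicability sentence:** add participants whose first BKZ dose is after the pandemic end date.
- **10.1.5.2:** replace *started IMP* with *received the first BKZ dose* in the branches that use it.
- **Throughout 10.1.5:** write *date of first BKZ dose* for *date of first dose*. Section 10.1.4 already uses the specific term, while section 3.3 bases the time of first dose on the first injection, active or not.

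The cost is a wording change in the SAP and a small programming change.

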10.2 Adverse events

Adverse events with start date prior to first administration of study medication are defined as pre-treatment AEs. No summaries of these events will typically be produced although they will be included in listings.

Adverse events that started more than 140 days after the last administration of study medication are defined as post-treatment AEs. Such events will not be included in any tabulated summaries but will be listed.

Treatment-emergent AEs (TEAEs) are defined as those AEs that have a start date on or following the first dose of study treatment through the final dose of study treatment + 140 days (covering the 20-week SFU period).

All summaries will be provided by treatment group. The treatment group for each study participant will be defined as the treatment received at the onset of the AE. If the onset of the AE occurs on the day where the study participant switches treatment from the Double-Blind Treatment Period to the Maintenance Period and receives a new treatment, it will be attributed to the originally randomized study treatment. The only exception to this is if the AE fulfills the criteria for an anaphylactic reaction. See Section 3.7 for further details.

AEs will be presented as “number of study participants (percentage of study participants) [number of events]”. In this style of output, “[number of events]” will include all cases of an AE including repeat occurrences in individual study participants, while “number of study participants” will count each study participant only once.

Adverse event summaries by SOC, HLT and PT will be ordered alphabetically for SOC and HLT within SOC and in terms of decreasing frequency for PT within HLT in the bimekizumab treatment group and then similarly by decreasing frequency in the placebo group.

AE summaries by PT will be ordered in terms of decreasing frequency for PT within the bimekizumab treatment group, and in the event of ties, PT will be sorted alphabetically.

Study participant time at risk represents the time a study participant is at risk for having an AE. The definitions for study participant time at risk (in days) are outlined in Section 10.1. These definitions will be used for exposure-adjusted AE summaries.

Selected AE summaries will include the exposure adjusted incidence rate (EAIR) with associated 95% confidence interval and the exposure adjusted event rate (EAER).

The EAIR is defined as the number of study participants (k) with a specific AE adjusted for the exposure and will be scaled to 100 subject-years:

$$\text{EAIR} = 100 \times \frac{k}{\sum_{i=1}^n (T_{\text{Exp}(i)})}$$

where n is the total number of study participants in the respective treatment group, and $T_{\text{Exp}(i)}$ is the time of exposure for each study participant defined as:

- For study participants with the specific AE of interest: years since first dose of the study treatment to the first occurrence for the AE of interest at the level of coding evaluated (see Section 10.1)
- For study participants without the AE: the time at risk in years (see Section 10.1)

Exact Poisson 95% confidence intervals for incidence rates are calculated using the relationship between the Poisson and the Chi-square distribution (Ulm, 1990; Fay and Feuer, 1997):

$$\begin{aligned} LCL &= \frac{\chi^2_{2n,\alpha/2}}{2} \\ UCL &= \frac{\chi^2_{2(n+1),1-\alpha/2}}{2} \end{aligned}$$

where n is the number of study participants with a specific AE for the incidence rate of interest and is the basis for the number of the degrees of freedom for the chi-square quantile for the upper tail probability χ^2 .

The EAER will be the number of AEs including repeat occurrences in individual study participants divided by the total time at risk scaled to 100 subject-years and calculated using:

$$\text{EAER} = 100 \times \frac{N_{AE}}{\sum_{i=1}^n (T_{\text{Risk}(i)})}$$

where N_{AE} is the total number of AEs, n is the total number of study participants and $T_{\text{Risk}(i)}$ is the time at risk in years for each study participant.

No confidence interval will be computed for EAER.

In the following sections, all tables based on “100 subject-years” will include EAIR (with 95% confidence interval) and EAER.

As previously indicated in [Table 4–3](#), the AE summary tables described in Section [10.2.1](#) and Section [10.2.2](#) will be presented:

- on the SS for the overall period, presenting the BKZ 160 mg Total treatment column only.
- on the SS for the Double-Blind Treatment Period for the Week 24 interim analysis only, presenting the Placebo and BKZ 160mg treatment columns.
- and on the MS for the Maintenance Period for the Week 52 interim analysis only, presenting the BKZ 160 mg Total treatment column only.

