3.3 Definition of Baseline values

A Baseline value for a study participant is defined as the latest measurement for that study participant up to and including the day of administration of first study medication (ie, generally Visit 2). When no treatment information is available, the randomization date will be used as reference in place of the first day of study drug administration. If a Baseline assessment is taken on the same day as first administration of study medication, it is eligible to be used as the Baseline value, even in the case that the time of the assessment is recorded as taking place after the time of first study medication administration. This is considered acceptable as this measurement is still the best representation of the Baseline value of the given assessment since it

is highly unlikely that the study medication could have an impact on any measurement in such a short period of time. However, such cases should be rare as study center personnel are instructed to do all assessments at the Baseline visit prior to administering study medication. One exception to this rule is plasma concentration. If Baseline plasma concentration is measured at a time after the first administration of study medication, then it should not be eligible to be considered as a Baseline plasma concentration. Such cases should be discussed with the quantitative clinical pharmacologist.

For HLA-B27 only, the Baseline value may be based on a value recorded after the first study medication administration because the study medication is not expected to have any impact on the HLA-B27 measurement.

If a Baseline measurement is missing or not collected, and a Screening value is available, the Screening value will be utilized as Baseline instead. If no measurement is available prior to receiving study medication, then the Baseline value is treated as missing. Finally, re-test value can be considered to define a Baseline, as mentioned in Section 3.1.

Baseline values for component scores should be computed using components from the same visit where the relevant measurements were recorded prior to dosing. However, if the Screening visit has all of the components, but the Baseline visit is missing one or more components, the Baseline value for the component score will be calculated using the Screening visit values.

When the time of first dose is derived, it should be based on the first injection of study treatment, regardless of whether or not it is an active treatment.

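### The EAIR rule gives event time no period-specific start, so the Maintenance Period rates come out too low if programmed as written

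*SAP*

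**What the plan says.** Section 10.2 divides the number of participants with an AE by summed exposure time, and that time is defined in two ways.

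- With the event: "years since first dose of the study treatment to the first occurrence for the AE of interest". The bullet continues "at the level of coding evaluated (see Section 10.1".
- Without the event: "For study participants without the AE: the time at risk in years (see Section 10.1".

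The section also says of the Section 10.1 time-at-risk definitions: "These definitions will be used for exposure-adjusted AE summaries".

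The same rule serves three sets of tables: the double-blind tables (placebo and bimekizumab columns), the overall tables (bimekizumab-total column), and a third set, "and on the MS for the Maintenance Period for the Week 52 interim analysis only, presenting the BKZ 160 mg Total treatment column only".

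Section 10.1 makes time at risk depend on the period. Every formula in Section 10.1.2 counts from the first dose of the Maintenance Period. Section 10.1.3 keeps a switcher's placebo time apart from the bimekizumab time that follows. For the time of first dose in general, Section 3.3 says "it should be based on the first injection of study treatment, regardless of whether or not it is an active treatment".

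**The concern.** The two halves of one denominator can start on different dates. In the maintenance table, event-free participants are counted from about Week 16. Read literally, participants with an event are counted from Day 1, although only maintenance events are tabulated.

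This gives odd results. A participant with an event on maintenance day 200 would contribute about 200 + 112 = 312 days, while an event-free completer who enters the extension contributes about 253. Having the event lengthens exposure.

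The excess grows with the number of participants affected, so common AEs and the any-TEAE row would be understated most. The error always makes bimekizumab rates look lower.

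**Working it through.** The SAP states no EAIR value, so there is no figure to reproduce.

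**Inputs from the SAP**
- Double-blind period: 112 days (Section 10.1.1), which is 16 × 7. In years, 112 / 365.25 = 0.3066.
- Planned numbers: 200 bimekizumab and 100 placebo, the latter moving to bimekizumab at Week 16 (Section 2.3).
- Maintenance time at risk (Section 10.1.2): 36 × 7 + 1 = 253 days for a completer who enters the extension; up to (48 − 16) × 7 + 140 + 1 = 365 days for others.

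**Assumptions not in the SAP:** constant hazard, no dropout, a range of true rates, 253 days at risk in maintenance, and 52 × 7 + 1 = 365 days overall for participants randomized to bimekizumab.

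**Maintenance table.** With hazard λ per year, expected person-time is k/λ for k participants with an event. The literal rule adds 0.3066 years to each, so

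literal rate = k / (k/λ + 0.3066 k) = λ / (1 + 0.3066 λ).

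At λ = 0.20 this is 0.20 / 1.0613 = 0.188, or 18.8 per 100 subject-years instead of 20. The number at risk and the length of follow-up cancel, so 253 or 365 days gives the same ratio.

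If study treatment is taken to mean bimekizumab, only the 200 of 300 randomized to bimekizumab are shifted, and 0.3066 becomes 0.3066 × 2/3.

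**Overall bimekizumab-total column.** For participants randomized to bimekizumab, Day 1 is the correct start. Only the 100 switchers can be shifted. At λ = 0.20 the expected participants with events are 36.23 (of 200, over 365 days) and 12.94 (of 100, over 253 days). Correct person-time is 49.17 / 0.20 = 245.8 years. The literal rule adds 12.94 × 0.3066 = 3.97 years, and 49.17 / 249.8 gives 19.7 per 100.

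| True rate per 100 subject-years | Maintenance, all shifted | Maintenance, only bimekizumab-randomized shifted | Overall, only switchers shifted |
|---|---|---|---|
| 5 | 4.92 (−1.5%) | 4.95 (−1.0%) | 4.98 (−0.4%) |
| 20 | 18.8 (−5.8%) | 19.2 (−3.9%) | 19.7 (−1.6%) |
| 50 | 43.4 (−13%) | 45.4 (−9.3%) | 48.0 (−4.0%) |
| 100 | 76.5 (−23%) | 83.0 (−17%) | 92.0 (−8.0%) |

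**Check without the hazard assumption.** Suppose 60 of 300 have a maintenance event at day 126 and 240 are event-free for 253 days. Correct: 100 × 60 / [(60 × 126 + 240 × 253) / 365.25] = 32.1. Literal: 126 becomes 238, giving 29.2, or 9.0% lower.

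**Unaffected.** In the double-blind table the first dose is the start of the period. The EAER uses total time at risk for every participant.

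**The case against.** The best defence is the cross-reference. Both bullets point to Section 10.1, whose time at risk depends on the period, and Section 10.2 says those definitions govern exposure-adjusted summaries. AEs are attributed to the treatment at onset, and switchers' placebo time is kept separate, so in a bimekizumab column study treatment can be read as bimekizumab. The Section 3.3 rule on first dose belongs to the definition of Baseline, and the TEAE definition ("have a start date on or following the first dose of study treatment through the final dose of study treatment + 140 days") decides which events count, not when person-time starts.

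Much of this stands as evidence of intent. It does not supply the missing start. Section 10.1 defines medication duration and time at risk but no origin for time to first event. Reading study treatment as bimekizumab does not rescue the maintenance table either: the first bimekizumab dose of participants randomized to bimekizumab is still Day 1.

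The defence does block some stronger inferences. A reader might conclude that every EAIR table is wrong; the double-blind table is not. A reader might conclude that bimekizumab-total rates carry 16 extra weeks for everyone with an event; in the overall table that could apply only to switchers. A reader might also take a figure near 30% as typical. It arises if 60% are affected at a mean onset of 90 days with 252 days of follow-up: 60 / [(0.6 × 90 + 0.4 × 252) / 365.25] = 142 against 60 / [(0.6 × 202 + 0.4 × 252) / 365.25] = 99. Those inputs are an assumed extreme. Finally, no randomized comparison is touched, because the affected tables show a bimekizumab-total column only.

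**Conclusion.** The point holds as a time origin that is not properly fixed. The understatement follows if the bullet is programmed as written; the SAP does not show that it will be.

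The main exposure is the maintenance table, by the amounts in the working: 1.5% to 6% at rates of 5 to 20 per 100 subject-years, rising to 23% at 100. If study treatment means bimekizumab these fall by roughly a third but do not vanish. The overall bimekizumab-total column is a lesser and conditional case. The sizes rest on constant hazard, no dropout and planned numbers. The direction does not depend on those assumptions. For rare events the effect is negligible.

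**What to change.** Replace the with-event bullet in Section 10.2 by: *years from the first dose in the period tabulated (first bimekizumab dose for the bimekizumab total column in the overall period) to the first occurrence of the AE in that period, at the level of coding evaluated.*

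This agrees with Sections 10.1.2 and 10.1.3 and leaves the double-blind tables unchanged. It needs no new data, only a line of SAP text and the matching program specification. Compared with literal programming, the downside is somewhat higher reported rates for common AEs in the maintenance table and, to a smaller degree, possibly in the overall one.
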